9. AMENDMENTS TO THE CLINICAL TRIAL PROTOCOL

All protocol amendments will be submitted to the Institutional Review Boards (IRBs) when any revision is made to the original protocol or subsequent version of the protocol that significantly affect the safety of subjects and/or any change is made that significantly affects the scope of investigation or scientific quality of the study.

The amended protocol will be reviewed, approved and documented by the same method in which the original protocol was reviewed and approved.

10. DEVICE ACCOUNTABILITY

Device accountability is ensured by Novocure through the following procedures:

- Shipping of clinical devices: SOP-USOC-003 Final release
- Use of clinical devices : SAP ERP
- Return of clinical devices : SOP-USOC-006 : Technical support-RMA Process

Appendix 1 Performance Status Criteria

ECOG Performance Status Scale		Karnofsky Performance Scale	
Grade	Descriptions	Percent	Description
0	Normal activity Fully active, able to carry on all pre-disease performance without restriction	100	Normal, no complaints, no evidence of disease
		90	Able to carry on normal activity; minor signs or symptoms of disease
1	Symptoms, but ambulatory Restricted in physically strenuous activity, but ambulatory and able to carry out work of a light or sedentary nature (e.g., light housework, office work)	80	Normal activity with effort; some signs or symptoms of disease
		70	Cares for self, unable to carry on normal activity or to do active work
2	In bed < 50% of the time Ambulatory and capable of all self-care, but unable to carry out any work activities Up and about more than 50% of waking hours	60	Requires occasional assistance, but is able to care for most of his/her needs
		50	Requires considerable assistance and frequent medical care
3	In bed > 50% of the time Capable of only limited self-care, confined to bed or chair more than 50% of waking hours	40	Disabled, requires special care and assistance
		30	Severely disabled, hospitalization indicated Death not imminent
4	100% bedridden Completely disabled Cannot carry on any self-care Totally confined to bed or chair	20	Very sick, hospitalization indicated Death not imminent
		10	Moribund, fatal processes progressing rapidly
5	Dead	0	Dead

Appendix 2 Acceptable Method of Birth Control

Women of child-bearing potential (WOCBP) and men able to father a child must agree to use highly effective contraception while on study treatment and for 60 days after the last dose of temozolomide or Optune™ use. WOCBP must have a negative pregnancy test within 28 days of initiation of study treatment. (Note: The effects of the temozolomide and Optune™ on the developing human fetus are unknown; thus, WOCBP and men able to father a child must agree to use 2 highly effective contraception methods). Highly effective contraception is defined as a method with a failure rate of less than 1 % per year, including but not limited to:

- a. True Abstinence: When this is in line with the preferred and usual lifestyle of the subject. Periodic abstinence (e.g., calendar, ovulation, post-ovulation methods) and withdrawal are not acceptable methods of contraception.
- b. Postmenopausal: Natural, spontaneous amenorrhea with an appropriate clinical profile for ≥ 1 year.
- c. Female Sterilization: Surgical bilateral oophorectomy, hysterectomy, or tubal ligation at least six weeks prior.
- d. Male Sterilization (provided the partner has received appropriate medical confirmation of the surgical success of the vasectomy). For female subjects on the study, the vasectomized male partner should be the sole partner for that participant.
- e. Use of a combination of any two of the following:
 1. Placement of an intrauterine device (IUD) or intrauterine system (IUS)
 2. Barrier methods of contraception: Condom or Occlusive cap (diaphragm or cervical/vault caps) with spermicidal foam/gel/film/cream/vaginal suppository
- f. Appropriate hormonal contraceptives (including any registered and marketed contraceptive agent that contains an estrogen and/or a progestational agent – including oral, subcutaneous, intrauterine, or intramuscular agents)

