2. MGMT methylation status and IDH mutation status must be assessed at the study site or patient's referral center. MGMT status will be used for stratification purposes but will not exclude patients from this study if they are either methylated, unmethylated, or indeterminate, or in process at the time of enrollment. Similarly, subjects with tumors that are IDH mutated or wild type are both eligible.
3. Supratentorial location
4. Maximum safe resection (including patients who can only safely be biopsied)
5. 22 years of age or older
6. Estimated survival of at least 12 weeks
7. KPS 70% or greater at time of entry to study
8. Patient provided written informed consent, or provided by a legally authorized representative
9. Willingness to comply with all procedures, including visits or evaluations, imaging, laboratory tests and rescue measures
10. Acceptable method of birth control (see appendix)
11. Have had a contrast-enhanced brain MRI after tumor resection procedure. If biopsy alone performed, cranial CT may be used in place of MRI, only if the patient had a preoperative MRI scan within 14 days of the biopsy.

12. The following time period must have elapsed prior to study enrollment: 3-6 weeks (21-42 days) from time of definitive surgery or 2-4 weeks (14-28 days) from the time of biopsy, for those who were only able to safely have a biopsy and not full resection.

Exclusion Criteria:

1. Craniotomy or stereotactic biopsy wound dehiscence or infection
2. Known by history to be HIV positive or to have an AIDS-related illness, active Hepatitis B, or active Hepatitis C (testing not required)
3. Presence of skull defects (bullets, metal fragments, missing bone)
4. Patients with implanted electronic medical devices (including but not limited to: pacemaker, vagal nerve stimulator, or pain stimulator)
5. Prior invasive malignancy, unless disease free for 3 or more years, with the exception of basal cell carcinoma, cervical carcinoma in situ, or melanoma in situ
6. Recurrent malignant gliomas or higher grade gliomas transformed from previous low grade (II) glioma
7. Patients with any current Primary brain stem or spinal cord tumor
8. Prior use of temozolomide
9. Prior treatment with Avastin

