3. Prospective participants will be pre-screened for the above inclusion and exclusion criteria. They will then undergo a screening pretreatment evaluation.

Screening

The following Screening procedures and assessments will start between Day -21 and Day 0.

- Obtain informed consent
- Vital signs: height (only at screening), weight, temperature, pulse, respiration rate, and resting blood pressure
- Demographic collection. To include: date of birth, gender, race, ethnicity, and education level
- Physical examination including neurologic exam and head and neck exam to evaluate surgical healing and contraindications to radiation and TTField therapy
- Complete medical history, including all prior and current conditions at the time of screening
- Smoking, alcohol, and substance use history
- Documentation of pathology proven glioblastoma or gliosarcoma
- Documentation of disease assessment, status and extent of measurable disease on imaging
- KPS (performance) assessment
- History of prior treatments and any residual toxicity relating to prior treatment
- Concomitant medication review and prior medications taken within 7 days of Day 1
- Confirmation of MGMT testing in process. If results are in process at time of screening, review at each subsequent visit until resulted.
- Documentation of IDH mutation status by immunohistochemistry or genetics. This is for classification of the tumors but not an exclusion criteria. If results in process at time of screening, review at each subsequent visit until resulted.
- Complete blood count (CBC) with differential and platelet count
- Blood chemistry assessment, including:
 - Alkaline phosphatase, aspartate aminotransferase/alanine aminotransferase (ALT/AST), total bilirubin, calcium, blood urea nitrogen (BUN), creatinine, total protein, albumin, fasting glucose, potassium, sodium, chloride, bicarbonate

- Coagulation assessment, including prothrombin time, partial thromboplastin time, international normalized ratio (PT/PTT/INR)
- Serum or urine pregnancy test (for women of childbearing potential)
- Confirmation of imaging (MRI) of the brain for tumor/lesion completed during pre-study period
- Review of Imaging (MRI) of the brain for tumor/lesion assessment, including collection and review of prior relevant brain MRIs

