7. SUBJECT ASSESSMENTS FOR SAFETY AND EFFICACY

The study procedure calendar for this study is provided in **Appendix 3**.

a) Evaluation of Safety and Tolerability**Dose Limiting Toxicity**

Dose limiting toxicities (DLTs) are defined as any severe or life-threatening treatment-related toxicity that precludes the use of a specified dose of any of the study treatments (TTFields, temozolomide, radiation) including continued use of Optune TTFields device at the standard treatment levels and schedule set out by prior studies. This study will prioritize preserving the standard of care for glioblastoma using approved dosing and radiation of temozolomide and radiation.

Toxicities will be graded according to the CTCAE (Version 5.0) scale. If multiple toxicities are seen, the presence of DLT should be based on the most severe toxicity experienced. Dose-limiting toxicities will be defined as any of the following events which occur during the experimental trimodal therapy with TTFields is added concurrently to radiation and temozolomide therapy or during the 8 weeks after RT is completed, and are considered by the investigator to be attributable to TTFields or the combination of TTFields with radiation and/or temozolomide:

- Any Grade > 3 thrombocytopenia, and Grade 4 anemia and neutropenia.
- Any nonhematologic Grade > 3 toxicity (including nausea, vomiting, or diarrhea), excluding alopecia.

- Any Grade 3-4 radiation-induced skin changes that persist for greater than 7 days and does not improve with management recommendations as outlined in toxicity management.
- Any adverse effect deemed by the investigator, patient's primary neuro-oncologist, or radiation oncologist to be life threatening in nature.

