Appendix 3 Study Calendar

Procedure/Visit	Pre-Study	Study Period (extends 8 weeks post RT/TMZ for DLT monitoring)					Long-Term Follow-up		Any time during Study Period	Any time during Study Period
	Pre-Consent	Screening	Trimodal Therapy (6-7 weeks)	Post RT/TMZ (4 weeks)	Adjuvant TMZ Therapy (Cycles are 28 days each)			Adjuvant TMZ Therapy Cycles 3-6 and beyond, if applicable	Maintenance TTField Therapy ^L	Any time during Study Period
		Day -21 to 0	Day 1	Day 8 +7 days; Day 15, 22, 29, 36, 43 ±7 days for each	Day 64 ±7 days	Cycle 1 (First cycle 1 begins on Day 78 ±5 days)	Cycle 2 (First cycle 2 begins on Day 106 ±5 days)	Minimum of 4 additional cycles		
Tumor Resection or Biopsy	X ^{DD}									
Informed Consent		X								
Demographics		X ^I								
Eligibility Review		X	X							
Medical History		X								
Treatment History/Toxicity Assessment		X ^M								
Disease Assessment/Extent of Measurable Disease		X ^D			X ^P	X ^{P, EE}	-----X ^{P, CC} -----			
Vital Signs ^Q		X ^A	X		X	X				X ^{GG}
Physical Exam		X ^B	X ^{B, H}		X ^K	X ^K	X ^K			X ^{GG}
Neuro Exam		X		X ^K						X ^{GG}
KPS		X	X		X	X	X			X ^{GG}
Objective Response					X	X ^{EE}	-----X ^{CC} -----			X ^{GG}
CBC w/diff & Platelet Count		X	X ^U	X	X	X	X			X ^{GG}
Blood Chemistry ^S		X	X ^U		X	X	X			X ^{GG}
Confirm MGMT Testing		X ^R								
Documentation of IDH status		X ^R								
Coagulation Assessment ^T		X								
Serum or Urine Preg Test		X								
ECG		X ^W								
MRI of the Brain w/wo Contrast ^O	X ^F				X ^{HH}					X ^{GG, HH}
Review of Imaging for Treatment Planning		X ^C								
Seizure & Headache Assessment ^I		X	X							
Radiation Oncology Planning		X								

Device Specialist			X ^G	X		X-----X-----				X ^{GG}	
TTField Compliance Review ^{FF}			X	X		X-----X-----		X-----X-----		X ^{GG}	X
TTField Therapy			X ^G	X	X	X	X	X-----X-----		X ^{GG}	
Radiation Therapy (RT)			X ^G	X ^{BB}						X ^{GG}	
Temozolomide (TMZ)			X ^G	X ^{BB}		X ^V	X			X ^{GG}	
Skin Exam			X	X ^{N, HH}	X ^{N, HH}	X ^{N, Y, HH}	X ^{N, Y, HH}			X ^{GG, HH}	
Con meds		X ^E			X-----X-----					X ^{GG}	X
Adverse Events ^{AA}				X-----X-----						X ^{GG}	X
Survival Documentation								X-----X ^Z -----			

A: To include height at screening.
B: Including neurologic exam, head exam, and neck exam.
C: Must be done within 14 days prior to Day 1.
D: At screening, to including documented pathology proven glioblastoma or gliosarcoma.
E: To include medications taken within 7 days of Day 1.

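### The single screening pregnancy test can be 35 days old at first temozolomide (42 on a looser reading), and Appendix 2 does not say whether its 28-day limit covers that dose

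*Combined protocol and SAP*

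**What the plan says.** **The limit.** Appendix 2 of the combined protocol and SAP says "WOCBP must have a negative pregnancy test within 28 days of initiation of study treatment". It names no component. Section 7a (Dose Limiting Toxicity) counts TTFields, temozolomide and radiation as study treatments.

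**The test.** It is listed once, under Screening in Section 6, and the calendar row "Serum or Urine Preg Test" in Appendix 3 is marked only in the screening column. On timing, Section 6 says "The following Screening procedures and assessments will start between Day -21 and Day 0". The lists for Day 1, Day 8 to Day 43, Day 64, the adjuvant cycles and unscheduled visits contain no pregnancy test.

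**The treatment windows** (Section 6, Treatment Period and the sequence diagram notes). The device starts between Day 1 and Day 8, and up to 14 days before RT/TMZ. RT starts by Day 15. Temozolomide ideally starts with RT, but up to 7 days later is acceptable, so by Day 22. The Day 8 visit is the nominal start for both RT and temozolomide.

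**A second screening limit.** The opening of Clinical Trial-Related Procedures in Section 6 allows screening assessments at most 21 days before first use of the investigational product.

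**Contraception.** Under Appendix 2, women of childbearing potential and men able to father a child "must agree to use highly effective contraception while on study treatment" and for 60 days after the last temozolomide or device use. The appendix gives the reason for two methods: the effects of temozolomide and the device "on the developing human fetus are unknown".

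**The concern.** The device, RT and temozolomide start on staggered dates, but the test is done once, before all of them. A limit tied to the start of study treatment is clear when everything starts together. Here it leaves open whether first temozolomide must also fall within 28 days of a negative test. If it need not, the protocol sets no limit on the age of the test at that dose. If it must, the permitted windows allow the limit to be exceeded and no repeat test is scheduled.

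At stake is possible fetal exposure in an early, undetected pregnancy. Pregnancy is not among the 20 exclusion criteria. Inclusion criterion 10 only refers to the birth-control appendix, so the sentence in Appendix 2 is the operative safeguard. The Day 1 visit already repeats CBC and chemistry unless they were done within 14 days, but the pregnancy test has no such rule.

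**Working it through.** **Day convention.** The Pre-Study list places resection at Day -42 to Day -21, and the Day 1 heading describes the same interval as 21 to 42 days from surgery. So Day -k is k days before Day 1, and Day n is n - 1 days after it. If Day 0 is counted as a separate day, ages measured from a calendar date before Day 0 rise by 1. Ages that come from the 21-day and 14-day rules do not change.

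**The plan's own figure.** Latest temozolomide start = Day 1 + 14 (RT) + 7 (temozolomide) = Day 22, as the sequence notes state.

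**Age at first device use.**
- Calendar alone: Day -21 to Day 8 = 21 + 7 = 28 days.
- 21-day rule: at most 21 days.

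A limit anchored to the device is therefore met.

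**Age at first temozolomide, resected patients, calendar window alone.**

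| Temozolomide start | Oldest test | Test dates giving more than 28 days |
|---|---|---|
| Day 8 (nominal) | 21 + 7 = 28 | none |
| Day 15 | 21 + 14 = 35 | Day -21 to Day -15 (7 dates) |
| Day 22 | 21 + 21 = 42 | Day -21 to Day -8 (14 dates) |

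**Adding the other two written limits.** Age at temozolomide = (test to device) + (device to temozolomide).
- Both bind: 21 + 14 = 35 days. Example: surgery Day -28, test Day -14, device Day 8, RT Day 15, temozolomide Day 22. RT is then 28 + 14 = 42 days after surgery, inside the 4 to 6 weeks allowed.
- The 21-day rule is read as running to the Day 1 visit: test Day -21, device Day 8, temozolomide Day 22 gives 28 + 14 = 42 days.
- The 14-day cap is read as limiting RT only: test Day -21, device Day 1, RT Day 15, temozolomide Day 22 gives 21 + 21 = 42 days.

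Under the 21-day rule, any gap of more than 7 days between device and temozolomide can take the age past 28.

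**Biopsy-only patients.** RT must start within 28 days of biopsy, and the test is assumed not to precede the biopsy. The age is then at most 28 days if temozolomide starts with RT, and at most 28 + 7 = 35 if it starts 7 days later. It is 34 if the test is at least one day after the biopsy, which the documents do not state.

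**Contraception.** It is required while on study treatment, hence from device start. The stretch not expressly covered is from the test to first device use: up to 21 days under the 21-day rule, 28 under the calendar. At device start the test is at most 28 days old, so every day beyond 28 falls after contraception has become mandatory.

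**The case against.** The strongest reply is that no rule is broken. The device normally starts first, so the start of study treatment is most naturally first device use, and on that reading the 28 days are always respected. This stands. A reader might infer that the protocol breaches its own limit or miscounts its windows. The documents support neither: the Day 22 figure is right, and whether a breach is possible depends on an anchor that Appendix 2 leaves open.

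A reader might also take 42 days as the plain maximum. It is not. It requires that either the 21-day screening rule or the 14-day cap be read loosely. With both applied as written the maximum is 35.

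A third tempting inference is that a woman could go five or six weeks between test and temozolomide with no protection. Contraception from device start rules that out, and eligibility, including the birth-control criterion, is reviewed again on Day 1. Both safeguards are real. Neither is a test, however: the review does not renew the result, and contraception from device start does not detect a conception that occurred between the test and that date.

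Two further points narrow the reach. On the nominal schedule, with temozolomide on Day 8, the oldest test is 28 days. The temozolomide section also refers to the package insert, and whether that or site practice prompts another test cannot be settled from these documents.

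**Conclusion.** The gap is real but of low severity. On the strictest reading of the timing rules, a resected patient's only pregnancy test can be 35 days old at first temozolomide, 7 days past the Appendix 2 figure. On looser readings it can be 42 days old. Biopsy-only patients reach 34 to 35 days, and only when temozolomide follows RT. Appendix 2 does not say whether its limit covers that dose.

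These are maxima. They need an early test and a late but permitted treatment start, and they apply only to women of childbearing potential in a trial of 30. They rest on the protocol's own day convention and, for biopsy-only patients, on the test not preceding the biopsy. The point concerns the scheduling of a safety check. Endpoints, stopping rules and analyses are unaffected.

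**What to change.** Do the pregnancy test at the existing Day 1 visit, with the result known before the device is started, either by moving the screening test there or by repeating it. The test is then at most 7 days old at first device use (Day 1 to Day 8) and 21 days old at a Day 22 temozolomide start. That is inside 28 days under every reading, so the questions about the 21-day rule and the 14-day cap need not be settled for this purpose. Copying the 14-day rule used for CBC and chemistry would not be enough: Day -14 to Day 22 is 14 + 21 = 35 days.

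In Appendix 2, state that the 28 days apply to both first device use and first temozolomide, and that contraception starts from the date of the test. Align the Screening and Day 1 lists in Section 6 and the Appendix 3 calendar.

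The cost is wording plus, if the test is repeated, one urine or serum test at a visit that already takes place, in women of childbearing potential only. Moving the test saves even that, but a pregnancy would then be found only after device planning has been done.

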Appendix 3 Study Calendar

Procedure/Visit	Pre-Study	Study Period (extends 8 weeks post RT/TMZ for DLT monitoring)					Long-Term Follow-up		Any time during Study Period	Any time during Study Period
	Pre-Consent	Screening	Trimodal Therapy (6-7 weeks)	Post RT/TMZ (4 weeks)	Adjuvant TMZ Therapy (Cycles are 28 days each)			Adjuvant TMZ Therapy Cycles 3-6 and beyond, if applicable	Maintenance TTField Therapy ^L	Any time during Study Period
		Day -21 to 0	Day 1	Day 8 +7 days; Day 15, 22, 29, 36, 43 ±7 days for each	Day 64 ±7 days	Cycle 1 (First cycle 1 begins on Day 78 ±5 days)	Cycle 2 (First cycle 2 begins on Day 106 ±5 days)	Minimum of 4 additional cycles		
Tumor Resection or Biopsy	X ^{DD}									
Informed Consent		X								
Demographics		X ^I								
Eligibility Review		X	X							
Medical History		X								
Treatment History/Toxicity Assessment		X ^M								
Disease Assessment/Extent of Measurable Disease		X ^D			X ^P	X ^{P, EE}	-----X ^{P, CC} -----			
Vital Signs ^Q		X ^A	X		X	X				X ^{GG}
Physical Exam		X ^B	X ^{B, H}		X ^K	X ^K	X ^K			X ^{GG}
Neuro Exam		X		X ^K						X ^{GG}
KPS		X	X		X	X	X			X ^{GG}
Objective Response					X	X ^{EE}	-----X ^{CC} -----			X ^{GG}
CBC w/diff & Platelet Count		X	X ^U	X	X	X	X			X ^{GG}
Blood Chemistry ^S		X	X ^U		X	X	X			X ^{GG}
Confirm MGMT Testing		X ^R								
Documentation of IDH status		X ^R								
Coagulation Assessment ^T		X								
Serum or Urine Preg Test		X								
ECG		X ^W								
MRI of the Brain w/wo Contrast ^O	X ^F				X ^{HH}					X ^{GG, HH}
Review of Imaging for Treatment Planning		X ^C								
Seizure & Headache Assessment ^I		X	X							
Radiation Oncology Planning		X								

Device Specialist			X ^G	X		X-----X-----				X ^{GG}	
TTField Compliance Review ^{FF}			X	X		X-----X-----		X-----X-----		X ^{GG}	X
TTField Therapy			X ^G	X	X	X	X	X-----X-----		X ^{GG}	
Radiation Therapy (RT)			X ^G	X ^{BB}						X ^{GG}	
Temozolomide (TMZ)			X ^G	X ^{BB}		X ^V	X			X ^{GG}	
Skin Exam			X	X ^{N, HH}	X ^{N, HH}	X ^{N, Y, HH}	X ^{N, Y, HH}			X ^{GG, HH}	
Con meds		X ^E			X-----X-----					X ^{GG}	X
Adverse Events ^{AA}				X-----X-----						X ^{GG}	X
Survival Documentation								X-----X ^Z -----			

A: To include height at screening.
B: Including neurologic exam, head exam, and neck exam.
C: Must be done within 14 days prior to Day 1.
D: At screening, to including documented pathology proven glioblastoma or gliosarcoma.
E: To include medications taken within 7 days of Day 1.
F: Confirmation of MRI completion within 3 days after tumor resection, with up to 5 additional days logistical delay being acceptable. If biopsy alone without full resection, cranial CT may be used instead of MRI, provided preoperative MRI completed within 14 days of biopsy.
G: TTF must start within 7 days of Day 1 and preferably a few days prior to beginning RT. TMZ must start within 7 days after beginning of RT. RT should be initiated no more than 14 days after Day 1.
H: To include scalp exam.
I: To include date of birth, gender, race, ethnicity, and education level.
J: Documentation of seizure frequency along with type of seizure (generalized or partial) and/or headache severity and frequency.
K: Including neurological exam, skin exam, and scalp assessment.
L: Obtained via chart review and by telephone (as needed) every 6 months until study completion.
M: To include history of prior treatments and any residual toxicity relating to prior treatment.
N: To include documentation of attribution, grade of toxicity, and if there is apparent correlation with the ceramic disc or adhesive gel on the transducer arrays.
O: With imaging assessment, status and extent of measurable disease on imaging. Repeat MRI every 2-3 months recommended.
P: Including clinical response or deterioration.
Q: Vitals to include: weight, temperature, pulse, respiration rate, and resting blood pressure.
R: MGMT methylation status and IDH mutation status must be assessed at the study site or patient's referral center. MGMT status will be used for stratification purposes but will not exclude patients from this study if they are either methylated, unmethylated, or indeterminate, or in process at the time of enrollment. Similarly, subjects with tumors that are IDH mutated or wildtype are both eligible. If results of MGMT and/or IDH are in process at time of screening, review at each subsequent visit until resulted.
S: To include alkaline phosphatase, ALT, AST, total bilirubin, calcium, blood urea nitrogen (BUN), creatinine, total protein, albumin, fasting glucose, potassium, sodium, chloride, bicarbonate.
T: To include PT, PTT, and INR.
U: If completed for screening within 14 days of Day 1, does not need to be repeated.
V: Cycle 1 day 1 dose is 150mg/m ² /day, all other cycles dose is 200mg/m ² /day.
W: To be collected and read by cardiology department.
X: To be done at Day 22 and Day 43 only.
Y: Day 1 of the first 2 cycles of adjuvant therapy will fall within the DLT window with continued skin exams (Cycle 1 Day 1 and Cycle 2 Day 1). The subsequent cycles with post-TMZ maintenance TTField therapy will proceed per the standard of care (minimum of 6 cycles, up to 2 years). For continued participation in the trial, patients must continue to follow up every 2-3 months with a repeat MRI of the brain.
Z: To include PFS and OS.
AA: Monitor adverse events through 8 weeks post-RT/TMZ (through Day 1 of first cycle of Cycle 2).
BB: To be stopped post Day 43 visit on Day 49 (+ 7 days, if clinically appropriate).
CC: To be assessed if MRI completed per SOC since last review/contact.
DD: Time that must have elapsed prior to study enrollment (Day 1): 3-6 weeks (21-42 days) from time of definitive surgery or 2-4 weeks (14-28 days) from the time of biopsy for those who were only able to safely have a biopsy and not full resection.
EE: Use MRI from Day 1 Cycle 1 for assessment.
FF: To be completed monthly, may not be available at each visit.
GG: If indicated, per investigator discretion.
HH: Transducer arrays will need to be removed/replaced to complete.

**Please note, the above notations can be found in the body of the protocol, but are listed here as well with the intent of making the study calendar easier to follow.*
